4.3.1.2 IOL Rotation

IOL rotation is defined as the difference in IOL axis of orientation from postoperative day 1. IOL rotation will be summarized by sample size, number, percent, and cumulative percent for the following categories of absolute rotation: <5 , <10 , <20 and ≥ 20 degrees. Additionally, descriptive statistics including the number of eyes, mean, median, standard deviation, minimum, maximum, and two-sided 95% CI of the mean will be reported for absolute value of IOL rotation. A listing of eyes with absolute IOL rotation of 10 degrees or more will also be presented.

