Subject population	
Adult Asian subjects, 20 years of age or older, who self-identify as being of Chinese, Japanese, Korean, or Mongolian descent, who require bilateral cataract extraction by phacoemulsification and have pre-existing corneal astigmatism, desire an IOL that provides the potential correction for near, intermediate and distance vision as well as for pre-existing corneal astigmatism.
 
Planned number of subjects enrolled/consented: 63 subjects Planned number of implanted subjects: 56 subjects Planned number of completed subjects: 50 subjects

Key inclusion criteria	
 • Planned bilateral cataract removal followed by posterior chamber IOL implantation with PanOptix Toric (TFNT30,

Analyses:

There are no statistical hypotheses for the safety and effectiveness objectives in this study.

Planned analyses include a descriptive summary of all effectiveness and safety endpoints up to Month 6. [REDACTED]

[REDACTED]

[REDACTED]

[REDACTED]

[REDACTED]. IOL rotation will be summarized by sample size, number, percent, and cumulative percent for the following categories of absolute rotation: (< 10 and < 20 degrees) for all models combined.

Descriptive statistics generated for all endpoints will be based upon the data type (ie, whether the data are categorical or continuous) being analyzed. For categorical endpoints, sample size, number in the category, and percent in the category will be presented. For continuous endpoints, sample size, mean, median, standard deviation, minimum, maximum, and two-sided 95% confidence intervals will be presented.

Visual acuity will be summarized as a continuous measure.

[REDACTED]

[REDACTED]

Sample Size Justification:

	
The choice of sample size is not based on statistical considerations.
 
Approximately 56 subjects will be bilaterally implanted to obtain data for at least 50 subjects (100 eyes) at Month 6, assuming a dropout rate of 10% over a 6-month period. The precision estimates below are presented for individual eye summaries. All eye summaries will have increased precision.
 
[Redacted text block]

Key words	Prospective, multi-center, single arm, postmarket study.
Associated materials	Surgical disposables used in conjunction with the IP (eg, OVDs, cartridges) as per the DFU and standard of care.

Table 3-1 Schedule of Study Procedures and Assessments

	Both Eyes	First Operative Eye			Second Operative Eye			Both Eyes		

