12.6.1.2 Analysis Methods

Rate of SSIs for either eye will be summarized by operative eye.

Descriptive summaries (counts and percentages) for rates of severe and most bothersome (separately) visual disturbances as reported by the subjects using the QUID questionnaire will be presented. These rates are accompanied by two-sided 95% CIs.

All AEs will be coded using the Medical Dictionary for Regulatory Activities (MedDRA). Ocular AEs will be summarized by operative eye. Descriptive tables (count and percentage) and listing will be generated for AEs based upon the categories of ocular and monocular AEs, serious and non-serious AEs, as appropriate.

[Redacted]

- [Redacted]
- [Redacted]
- [Redacted]
- [Redacted]
- [Redacted]
- [Redacted]
- [Redacted]
- [Redacted]

[Redacted]

[Redacted]

[Redacted]

[Redacted]

[Redacted]

[Redacted]

[Redacted]

[REDACTED]

[REDACTED]

[REDACTED]

[REDACTED]

[REDACTED]

[REDACTED]

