4.1 Efficacy Endpoints

All effectiveness endpoints will be summarized as follows for each visit, with Month 3 and 6 visit results being the key endpoint.

Key Endpoints

- Mean monocular residual manifest cylinder for all operative eyes
- Percent of IOLs with < 10 degree rotation for all operative eyes (rotation defined as the difference in IOL axis of orientation from postoperative day 1)
- Mean binocular BCDVA at 4m in photopic lighting condition
- Mean binocular DCIVA at 60cm in photopic lighting condition
- Mean binocular DCNVA at 40 cm in photopic lighting condition

[Redacted text block containing multiple paragraphs of obscured content]

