4.3 Statistical Methods for Efficacy Analyses

4.3.1 Analysis of Key Effectiveness Endpoints

4.3.1.1 Residual Manifest Cylinder

Monocular residual manifest cylinder will be summarized by visit for first operative eye, second operative eye and all eyes. The descriptive statistics including the number of eyes, mean, median, standard deviation, minimum, maximum, and two-sided 95% CI of the mean will be presented. Additionally, the number and percent of eyes will be presented for residual manifest cylinder in the following categories: within 0.25 D, within 0.50 D, within 1.00 D and more than 1.00 D.

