4.3.1.3 Binocular Photopic BCDVA, DCIVA and DCNVA

Binocular photopic BCDVA, DCIVA and DCNVA will be summarized as continuous variables with number of subjects, mean, median, standard deviation, minimum, maximum, and two-sided 95% confidence interval for the mean based on Student's *t* statistics, and will be presented at each visit the endpoints are collected. SAS PROC MEANS will be used to generate the confidence interval with option ALPHA=0.05.

For all visual acuity endpoints, the number and percentage of subjects in each of the following visual acuity categories will be presented:

The number and percentage of eyes with visual acuity of

- 0.00 logMAR or better: ≤ 0.00 logMAR

- 0.10 logMAR or better: ≤ 0.10 logMAR
- 0.20 logMAR or better: ≤ 0.20 logMAR
- 0.30 logMAR or better: ≤ 0.30 logMAR
- Worse than 0.30 logMAR: > 0.30 logMAR

[Redacted text block containing multiple lines of blacked-out content]

[REDACTED]

[REDACTED]

[REDACTED]

[REDACTED]

5 Safety Analysis Strategy

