5.3.3 Adverse Events

[figure not shown]
All adverse events (AEs) occurring from when a subject signs informed consent to when a subject exits the study will be accounted for in the reporting. Summary tables for AEs will include the number of affected eyes/subjects, percentage of affected eyes/subjects, 95% two sided confidence intervals, and the number of events. The number and percentage of ocular AEs will be provided for first and second operative eyes and for all eyes. An eye/subject with multiple AEs of the same preferred term will be counted only once toward the total of this preferred term. Listings of AEs will include the lens model, subject ID, Age/Sex, days from surgery, adverse event description, the MedDRA preferred term of the adverse event, and the causality assessment, severity, duration and outcome, when available. Surgery eye and the eye with AE will be provided in the listing of ocular AEs. Adverse events related to the IOL are referred to as adverse device effects (ADE). Listing of pre-treatment AEs, or AEs for non-study eyes will be provided if such cases exist.

Treatment emergent adverse events will be summarized in the following tables and listings:

- Table of All Adverse Events (Serious and Non-Serious Combined)
 - Ocular
 - Non-ocular
- Table of All Adverse Device Effects
 - Ocular
 - Non-ocular
- Table of All Serious Adverse Events (including Serious Adverse Device Effects)
 - Ocular
 - Non-ocular
- Listing of Adverse Event
 - Serious Ocular
 - Serious Non-ocular
 - Non-Serious Ocular
 - Non-Serious Non-ocular

6 Sample Size and Power Calculations

The choice of sample size is not based on statistical considerations.

Approximately 56 subjects will be bilaterally implanted to obtain data for at least 50 subjects (100 eyes) at Month 6, assuming a dropout rate of 10% over a 6 month period. The precision estimates below are presented for individual eye summaries. All eye summaries will have increased precision.

For visual acuity, with a sample size of 50 eyes and assuming a standard deviation of 0.18 logMAR [REDACTED] a two-sided 95%

confidence interval based on large sample z statistics will extend 0.05 logMAR from the observed mean.

[figure not shown]
For residual cylinder, a two-sided 95% confidence interval based on large sample z statistics will extend 0.11 D from the observed mean, assuming a standard deviation of 0.40 D [REDACTED]

[figure not shown]

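### Must the SAP add a confidence interval for the percent of lenses rotated less than 10 degrees, and a Month 3 cut and counting rule for SSIs?

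*SAP*

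**What the plan says.** **Rotation.** SAP 4.1 lists the key endpoint as "Percent of IOLs with < 10 degree rotation for all operative eyes". SAP 4.3.1.2 states that "IOL rotation will be summarized by sample size, number, percent, and cumulative percent for the following categories of absolute rotation", with cut points at 5, 10 and 20 degrees. It adds descriptive statistics and a 95% interval for mean absolute rotation, and then "A listing of eyes with absolute IOL rotation of 10 degrees or more will also be presented". The other four primary endpoints are means and have intervals: for residual cylinder, "two-sided 95% CI of the mean will be presented" (SAP 4.3.1.1), and for the three binocular acuities, a "two-sided 95% confidence interval for the mean based on" Student's *t* (SAP 4.3.1.3).

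The general rule is in the Protocol Summary: "For categorical endpoints, sample size, number in the category, and percent in the category will be presented". It names confidence intervals for continuous endpoints only.

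**SSIs.** Protocol 6.2 and SAP 1.1 set the objective as a cumulative SSI rate at Month 3 and Month 6. Protocol 12.6.1.2 makes the operative eye the reporting level. SAP 5.3.1 plans a number and percentage for first, second and all eyes in four categories of relationship to the lens. It also plans a listing that carries subject, eye, days from surgery and relationship.

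**Elsewhere in the safety plan**, percentages do get intervals. Of the QUVID rates, Protocol 12.6.1.2 says "These rates are accompanied by two-sided 95% CIs". The adverse event tables in SAP 5.3.3 give "percentage of affected eyes/subjects, 95% two sided confidence intervals, and the number of events".

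**The concern.** Four of the five primary endpoints come with an interval for the quantity they are defined by. Rotation does not: its interval is for the mean angle, which is a different quantity from the percent under 10 degrees. The protocol's rule for categorical endpoints does not look like a ban on intervals, because QUVID and adverse event percentages have them.

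For SSIs, the objective names two time points and the table has none. A count of interventions and a count of eyes with at least one intervention can differ, and SAP 5.3.1 does not choose between them.

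At stake would be a primary proportion printed without its precision, and a named Month 3 safety rate that the reader would have to assemble.

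**Working it through.** **1. The plan's own figures.** Protocol 12.8 and SAP 6 give precision at 50 eyes.

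- Acuity: 1.96 × 0.18/√50 = 0.0499 logMAR (stated 0.05).
- Cylinder: 1.96 × 0.40/√50 = 0.1109 D (stated 0.11).
- No events in 50 eyes: 1 − 0.05^(1/50) = 5.82% (stated as below 6%). This is the one-sided 95% limit. The two-sided one is 1 − 0.025^(1/50) = 7.11%.

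All three reproduce. The plan gives no precision figure for the rotation percent or for a Month 3 SSI rate.

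**2. What an interval for rotation would add.** The documents give no expected rotation rate and no between-eye correlation, so the counts below are assumed. The two-sided exact (Clopper–Pearson) limits for x of n are the 2.5% point of Beta(x, n − x + 1) and the 97.5% point of Beta(x + 1, n − x). The left interval treats 100 eyes as independent. The right one treats fellow eyes as identical, so 50 subjects are the units.

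| Eyes under 10 degrees | Independent eyes | Identical fellow eyes |
|---|---|---|
| 98/100 (49/50 subjects) | 92.96% to 99.76% | 89.35% to 99.95% |
| 96/100 (48/50 subjects) | 90.07% to 98.90% | 86.29% to 99.51% |

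Between these extremes the lower limit moves by just under 4 percentage points. The planned table prints the count and the denominator. The planned listing shows every eye at or above 10 degrees. If that listing identifies the subject, as listings normally do, a reader can also see whether rotated lenses come in pairs.

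**3. Is the rotation table out of line?** The other categorical summaries of effectiveness, the cylinder bands in SAP 4.3.1.1 and the acuity bands in SAP 4.3.1.3, have no intervals either. The four primary endpoints that do have intervals are means. The SAP is therefore applying the protocol's rule evenly across effectiveness.

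**4. SSIs: the counting unit.** The eye is the stated level, so the denominator is implied; only the numerator is open. With 56 × 2 = 112 eyes, one eye with two interventions gives 2/112 = 1.79% by interventions and 1/112 = 0.89% by eyes.

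**5. SSIs: the interval.** Two affected eyes in 112 give 0.22% to 6.30% if independent. If both belong to one subject (1/56), the exact interval is 0.05% to 9.55%. Protocol 11.2 makes every SSI except posterior capsulotomy a serious adverse event. Most SSIs therefore also enter the SAP 5.3.3 tables, which count affected eyes and events and give two-sided 95% intervals. Those tables do not show the optical-property category or a Month 3 cut.

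**6. SSIs: the Month 3 cut.** Month 6 is the end of follow-up, so the planned totals in effect serve it. Month 3 is Visit 4A, 90 to 120 days after the second surgery. The listing gives days from surgery, so nearly every SSI can be placed before or after that visit. For a first eye operated on 7 to 14 days earlier, as recommended, the window is 90 + 7 = 97 to 120 + 14 = 134 days from its own surgery. Only an SSI inside the window would need the actual visit date, which the database holds.

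**The case for a change.** The strongest case for a change is that a primary proportion deserves its interval, and that the reader's substitute is imperfect. SAP 4.3.1.2 shows no split by first and second eye, so the pooled count alone does not yield a valid interval when each subject contributes two eyes. Naming a method in advance would also prevent a choice made after seeing the data. The Month 3 SSI rate is a named objective with no visible table. Protocol 7.2 intends the results as supplementary data for regulatory approval, where complete tables are useful.

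Some of this stands. The percent under 10 degrees has no interval in the visible text, and SAP 5.3.1 states neither the Month 3 cut nor the numerator. Much of its weight goes, however. Rotation is not left without any statement of uncertainty, since the mean absolute angle has an interval and every eye at or above 10 degrees is listed. The serious adverse event tables cover most SSIs with intervals.

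The obvious remedy is not clean either. An interval that simply clusters on subject with a robust variance has zero width when all lenses are stable or no SSI occurs. At 98/100 with both rotated lenses in one subject, 50 subject means (49 at 1, one at 0) have variance 0.98 × 0.02 × 50/49 = 0.02. The standard error is √(0.02/50) = 0.02, and 98% ± 1.96 × 2% runs from 94.1% to 101.9%, beyond 100%.

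**Conclusion.** No change follows. These are gaps in reporting detail, and no rule as written produces a wrong result. The rotation table complies with the protocol. SAP Decision Criteria for Study Success is not applicable and SAP 4.2 plans no hypothesis test, so no conclusion turns on an interval or on a Month 3 SSI row. The data for both are collected and listed.

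A programmer preparing the SSI table would have to pick a numerator. Eyes with at least one SSI is the natural reading, given the operative eye as reporting level and the count-once convention by preferred term in SAP 5.3.3. In the examples the choice moves the rate by 0.9 percentage points, and full correlation between eyes moves the lower rotation limit by just under 4 points.

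This rests on assumed counts, on correlations of 0 and 1 as extremes, on listings that identify the subject, and on the visible text only. Sizeable blocks near Protocol 12.4.1.2 and 12.6.1.2 and SAP 4.1 and 5.1 are redacted and may contain a general rule on intervals or eye groups.

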4.3.1.3 Binocular Photopic BCDVA, DCIVA and DCNVA

Binocular photopic BCDVA, DCIVA and DCNVA will be summarized as continuous variables with number of subjects, mean, median, standard deviation, minimum, maximum, and two-sided 95% confidence interval for the mean based on Student's *t* statistics, and will be presented at each visit the endpoints are collected. SAS PROC MEANS will be used to generate the confidence interval with option ALPHA=0.05.

For all visual acuity endpoints, the number and percentage of subjects in each of the following visual acuity categories will be presented:

The number and percentage of eyes with visual acuity of

- 0.00 logMAR or better: ≤ 0.00 logMAR

- 0.10 logMAR or better: ≤ 0.10 logMAR
- 0.20 logMAR or better: ≤ 0.20 logMAR
- 0.30 logMAR or better: ≤ 0.30 logMAR
- Worse than 0.30 logMAR: > 0.30 logMAR

[Redacted text block containing multiple lines of blacked-out content]

[REDACTED]

[REDACTED]

[REDACTED]

[REDACTED]

5 Safety Analysis Strategy

5.1 Safety Endpoints

Key Endpoints:

- Rate of SSIs (including rate of SSIs related to optical properties of the IOL and rate of all SSIs)
- Rates of severe and most bothersome (separately) visual disturbances reported by QUVID questionnaire for subjects with binocular implantation by visit
- Rates of adverse events

[REDACTED]

[REDACTED]

5.2 Safety Hypotheses

There are no formal safety hypotheses in this study. The focus of the safety analysis will be a comprehensive descriptive assessment of the safety endpoints listed in Section 5.1.

5.3 Statistical Methods for Safety Analyses

5.3.1 Secondary Surgical Interventions

The number and percentage of secondary surgical interventions (SSIs) will be presented for first implanted eyes, second implanted eyes and for all eyes combined in each of the following categories relative to the relationship to IOL:

- 1) Overall
- 2) Related to IOL - due to optical properties
- 3) Related to IOL - not due to optical properties
- 4) Unrelated to IOL

A listing of SSIs will be presented. The listing will include all SSI data with the following variables: Lens model, subject, age, sex, race, specific Asian race, surgery eye, eye, days from surgery, relationship, and description.

5.3.2 Questionnaire for Visual Disturbances (QUVID)

Descriptive summaries (counts and percentages) for rates of severe and most bothersome (separately) visual disturbances as reported by the subjects using the QUVID questionnaire will be presented per user manual. These rates will be accompanied by two-sided 95% CIs.

The number and percentages of subjects in each category of responses to each question on the QUVID questionnaire will be reported at each visit this questionnaire is administered per user manual.

[figure not shown]
A listing of subjects with severe or most bothersome visual disturbance at any postoperative visit will be presented. A listing of subjects with other visual symptom not mentioned in the QUID will also be presented.

[figure not shown]
5.3.3 Adverse Events

[figure not shown]
All adverse events (AEs) occurring from when a subject signs informed consent to when a subject exits the study will be accounted for in the reporting. Summary tables for AEs will include the number of affected eyes/subjects, percentage of affected eyes/subjects, 95% two sided confidence intervals, and the number of events. The number and percentage of ocular AEs will be provided for first and second operative eyes and for all eyes. An eye/subject with multiple AEs of the same preferred term will be counted only once toward the total of this preferred term. Listings of AEs will include the lens model, subject ID, Age/Sex, days from surgery, adverse event description, the MedDRA preferred term of the adverse event, and the causality assessment, severity, duration and outcome, when available. Surgery eye and the eye with AE will be provided in the listing of ocular AEs. Adverse events related to the IOL are referred to as adverse device effects (ADE). Listing of pre-treatment AEs, or AEs for non-study eyes will be provided if such cases exist.

Treatment emergent adverse events will be summarized in the following tables and listings:

- Table of All Adverse Events (Serious and Non-Serious Combined)
 - Ocular
 - Non-ocular
- Table of All Adverse Device Effects
 - Ocular
 - Non-ocular
- Table of All Serious Adverse Events (including Serious Adverse Device Effects)
 - Ocular
 - Non-ocular
- Listing of Adverse Event
 - Serious Ocular
 - Serious Non-ocular
 - Non-Serious Ocular
 - Non-Serious Non-ocular

6 Sample Size and Power Calculations

The choice of sample size is not based on statistical considerations.

Approximately 56 subjects will be bilaterally implanted to obtain data for at least 50 subjects (100 eyes) at Month 6, assuming a dropout rate of 10% over a 6 month period. The precision estimates below are presented for individual eye summaries. All eye summaries will have increased precision.

For visual acuity, with a sample size of 50 eyes and assuming a standard deviation of 0.18 logMAR [REDACTED] a two-sided 95%

confidence interval based on large sample z statistics will extend 0.05 logMAR from the observed mean.

[figure not shown]
For residual cylinder, a two-sided 95% confidence interval based on large sample z statistics will extend 0.11 D from the observed mean, assuming a standard deviation of 0.40 D [REDACTED]

[figure not shown]
For any event where a zero incidence is observed in 50 eyes implanted with study IOL, the upper exact binomial 95% confidence limit is less than 6%. Thus, with 95% confidence, the true adverse event rate is less than 6%.

7 **References**

None.

8 **Revision History**

9 Appendix

Table 9-1 Schedule of Study Procedures and Assessments

	Both Eyes	First Operative Eye			Second Operative Eye			Both Eyes		
	Visit 0 (Preop)	Visit 00 (Op)	Visit 1 Day 1 - 2	Visit 2 Day 7 - 14	Visit 00A (Op)*	Visit 1A Day 1 - 2	Visit 2A Day 7 - 14	Visit 3A Day ¹ 30-60	Visit 4A Day ¹ 90-120	Visit 5A Day ¹ 180-210
Informed Consent	X									
Demographics	X									
Medical History ³	X									
Concomitant Medications ³	X	X	X	X	X	X	X	X	X	X
Urine Pregnancy Test ²	X									
Inclusion/Exclusion	X	X			X					
Ocular Biometry (Axial Length, Keratometry, Anterior Chamber Depth with corneal thickness, lens thickness, white-to-white)	X									X
ALCON® Online Toric IOL Calculator (Barrett) (Intended Axis Placement)	X									
Actual axis of IOL orientation			X ¹			X ²			X	X
██████████ ██████	■								■	■
██████████	■						■			
Target (Predicted) Residual Refractive Error (include spherical and cylinder)	X									
Administer Treatment(s)		X ¹			X ²					
Operative Eye		X ¹			X ²					
Surgical Problems		X ¹			X ²					
Other Procedures at Surgery		X ¹			X ²					
Incision Site		X ¹			X ²					
Final Incision Size		X ¹			X ²					
Lens Information		X ¹			X ²					
IOL Damage		X ¹			X ²					

		Both Eyes	First Operative Eye			Second Operative Eye			Both Eyes		
		Visit 0 (Preop)	Visit 00 (Op)	Visit 1 Day 1 - 2	Visit 2 Day 7 - 14	Visit 00A (Op)*	Visit 1A Day 1 - 2	Visit 2A Day 7 - 14	Visit 3A Day ¹ 30-60	Visit 4A Day ¹ 90-120	Visit 5A Day ¹ 180-210
Manifest Refraction		X			X ¹			X ²	X	X	X
Distance Visual Acuity (4 m) in photopic condition		■		■	■		■	■	■	■ ■	■ ■
	Best Corrected	■			■			■	■	■ X ^b	■ X ^b
										■ ■	■ ■
Intermediate Visual Acuity (60 cm) in photopic condition									■	■ ■	■ ■
	Distance Corrected								■	■ X ^b	■ X ^b
Near Visual Acuity (40 cm) in photopic condition									■	■ ■	■ ■
	Distance Corrected								■	■ X ^b	■ X ^b
										■ ■	■ ■
									■		■
Slit Lamp Examination		X		X ¹	X ¹		X ²	X ²	X	X	X
Dilated Fundus Examination		X			X ¹			X ²	X	X	X
		■								■	■
QUVID Subject Survey		X ^b								X ^b	X ^b
Secondary Surgical Interventions				X ¹	X ¹		X ²	X ²	X	X	X
			■	■	■	■	■	■	■	■	■
Adverse Events ⁵		X	X	X	X	X	X	X	X	X	X

NOTE:

* IOL implantation in the second eye is recommended to occur within 7-14 days from first eye implantation.

X: The 1st operative eye and the 2nd operative eye (if applicable) separately

X¹: Only the 1st operative eye

X²: Only the 2nd operative eye (if there is a 2nd operative eye)

X^b: Binocular examination (if there is a 2nd operative eye)

¹ Based on the 2nd eye post-operative surgery date (Visit 00A)

² In women of child bearing potential only

³ Refer to Section 9.6 and Section 9.6, eCRF Guidelines, and MOP for collection and documentation requirements. Concomitant medications and medical history must be fully documented in the subject source documents. eCRF data will be Targeted:

- Medical History: All ocular history, targeted systemic history*
 - Concomitant Medications: All ocular medications, targeted systemic medications
- *Pre-populated dropdown field

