12.8 Sample Size Justification

The choice of sample size is not based on statistical considerations.

Approximately 56 subjects will be bilaterally implanted to obtain data for at least 50 subjects (100 eyes) at Month 6, assuming a dropout rate of 10% over a 6 month period. The precision estimates below are presented for individual eye summaries. All eye summaries will have increased precision.

For visual acuity, with a sample size of 50 eyes and assuming a standard deviation of 0.18 logMAR [REDACTED] a two-sided

95% confidence interval based on large sample z statistics will extend 0.05 logMAR from the observed mean.

For residual cylinder, a two-sided 95% confidence interval based on large sample z statistics will extend 0.11 D from the observed mean, assuming a standard deviation of 0.40 D [REDACTED]

For any event where a zero incidence is observed in 50 eyes implanted with study IOL, the upper exact binomial 95% confidence limit is less than 6%. Thus, with 95% confidence, the true adverse event rate is less than 6%.

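### Is the 6% upper limit for zero events in 50 eyes wrong, given that the safety tables use two-sided 95% intervals?

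*SAP*

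**What the plan says.** The statement appears in the same form in SAP section 6 and Protocol section 12.8. It is conditional on a zero count among 50 eyes, and for that case both documents state that "the upper exact binomial 95% confidence limit is less than 6"%. The conclusion drawn is "Thus, with 95% confidence, the true adverse event rate is less than 6"%. Neither document says whether the limit is one-sided or two-sided.

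Three other places bear on the reading:

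- **Neighbouring precision figures.** The visual acuity and cylinder statements in the same sections are labelled two-sided, for example "For residual cylinder, a two-sided 95% confidence interval based on large sample z statistics will extend 0.11 D from the observed mean". All three figures refer to first eyes or second eyes taken separately: "The precision estimates below are presented for individual eye summaries".
- **Adverse event tables (SAP 5.3.3).** "Summary tables for AEs will include the number of affected eyes/subjects, percentage of affected eyes/subjects, 95% two sided confidence intervals".
- **QUVID (SAP 5.3.2).** "These rates will be accompanied by two-sided 95% CIs".

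The visible text of SAP 5.3.2 and 5.3.3 does not name the method for these intervals. The exact binomial method is named only in the sample size section.

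**The concern.** A reader who has just met two figures labelled two-sided 95% will take the third in the same way. Read so, it fails: the two-sided exact 95% interval for 0 of 50 reaches 7.1%, not a value below 6%. The adverse event and QUVID summaries are also committed to two-sided intervals, so a zero count in 50 could appear in the report with a higher upper limit than the planning section suggests.

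This is the only safety precision figure in the visible text, and the protocol intends the data to support Health Authority submissions. If the figure were wrong, the documents would overstate what 50 eyes can rule out.

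**Working it through.** **Inputs.** Zero events in 50 eyes (SAP section 6, Protocol 12.8). Planned: 56 subjects implanted bilaterally and 50 completing Month 6. The Safety Analysis Set contains all eyes with attempted implantation (SAP 2.2), so about 56 first eyes, 56 second eyes and 112 eyes overall.

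**Step 1: reproduce the plan's figure.** With zero events, the exact one-sided 95% upper bound solves (1 − p)^n = 0.05, so p = 1 − 0.05^(1/n). For n = 50, p = 1 − 0.05^(1/50) = 5.82%. This is below 6%, as stated. As a check, at a true rate of 6% the chance of no events is 0.94^50 = 0.0453. That is below 0.05, so 6% is excluded at the one-sided 5% level.

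**Step 2: the two-sided counterpart.** The exact two-sided 95% interval puts 2.5% in each tail, so the upper limit is 1 − 0.025^(1/n). For n = 50 it is 7.11%. The value 0.0453 from step 1 exceeds 0.025, so 6% is not excluded on this basis. The difference is 7.11 − 5.82 = 1.29 points.

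**Step 3: the neighbouring figures.** 1.96 × 0.18/√50 = 0.050 logMAR and 1.96 × 0.40/√50 = 0.111 D. Both reproduce as two-sided 95% half-widths, so the conventions within the section do differ.

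**Step 4: the denominators the safety tables would use.**

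| Eyes with zero events | One-sided exact 95% | Two-sided exact 95% |
|---|---|---|
| 50 | 5.82% | 7.11% |
| 56 (first or second eyes) | 5.21% | 6.38% |
| 112 (all eyes, treated as independent) | 2.64% | 3.24% |

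Fellow eyes are correlated. If each pair carried no more information than one eye, the all-eyes limit would go back to the 56-eye value, so the two-sided limit lies between about 3.2% and 6.4%. For the two-sided exact limit to fall below 6%, n must exceed ln(0.025)/ln(0.94) = 59.6, that is 60 eyes.

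**Step 5: dependence on the interval method.** The method is not named for the tables, so the two-sided 95% upper limit for 0 of 50 is a range:

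- Jeffreys: the 97.5% point of Beta(0.5, 50.5) = 4.88%
- Mid-P: 0.5(1 − p)^50 = 0.025, so p = 5.82%
- Clopper-Pearson: 7.11%
- Wilson: 1.96²/(50 + 1.96²) = 3.84/53.84 = 7.13%

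Two of these four fall below 6% and two above.

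**The case for a change.** The case for a correction is a fair one. The section names the exact binomial method. If the tables use it too, a zero count in 50 will be printed as 0% to 7.1%, and no safety output in the visible text uses a one-sided bound. The larger safety set narrows the gap without closing it: 56 eyes still give 6.4%. QUVID is answered per subject, and with 50 completers at Month 6 a zero count there would carry the 7.1% limit. Labelling the bound would take one word in each document.

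What stands is that the convention changes without a label, beside two figures that have one. What does not stand is that the figure is wrong or that the plan promises something it cannot deliver:

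- The sentence is an illustration about eyes and adverse event rates. It does not specify a table and does not concern QUVID.
- With zero events the lower limit is zero, so a one-sided upper bound is a natural choice, and the wording that follows is a one-sided claim.
- Putting the two-sided figure into that claim would not sharpen it. 7.1% is a one-sided 97.5% bound, so attaching 95% confidence to it would understate the confidence achieved.

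**Conclusion.** No change to the plan is needed. The 6% figure is correct as a one-sided exact 95% bound (5.8%), and the sentence built on it is true as written. What is missing is a label, which a statistician can supply by inverting the number.

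The size of the discrepancy is 1.3 points for 50 eyes if the two-sided exact method is assumed. For about 56 eyes the two-sided limit is 0.4 points above the stated 6%. For all eyes combined it lies between about 3.2% and 6.4%, depending on the correlation between fellow eyes. Mid-P or Jeffreys intervals would fall below 6% even at 50 eyes.

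Nothing rests on the figure. Both documents disclaim a statistical basis for the sample size, no safety hypothesis is planned, and the SAP lists success criteria as not applicable. The adverse event and QUVID summaries will carry two-sided 95% intervals computed from the observed counts and denominators, so readers of the report will see the two-sided limits directly. Adding the word one-sided would be harmless editing, but it would alter no result and no conclusion. This assumes that the redacted SAP text attaches no decision to the 6% figure.
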